#### **Statistical methods**

- a) Statistical analysis will be carried out using SPSS software.
- b) In inferential statistical analysis, the normality of the distribution of quantitative variables will be determined by the Kolmogorov-Smirnov test. For variables with normal distribution, the T-sudent test will be used and for those that do not have normal distribution, the Mann-Whitney test will be performed, with the purpose of analysing the statistical significance of the difference between the groups with IC 95% (positive MGPT and negative MGPT). For qualitative variables, the statistical significance of the difference between groups, with 95% CI, will be calculated using the Chi-square test (if more than 10% of the cells in the 2x2 tables have frequencies  $\leq 5$ ) or the Exact Fisher Test.

We will later perform a multivariate analysis with logistic regression to control confounding variables.

- c) Missing data: We addressed missing data by employing multiple strategies. Firstly, we conducted a thorough examination of patterns of missingness to discern if they followed a missing completely at random, missing at random, or missing not at random pattern. Subsequently, for cases with missing data, we utilized multiple imputation techniques to impute missing values based on observed data and variables that were predictive of missingness. Additionally, we performed sensitivity analyses to assess the robustness of our findings to different assumptions regarding the missing data mechanism. Overall, these

approaches allowed us to minimize bias and maintain the integrity of our analyses in the presence of missing data.

d) To conduct sensitivity analysis for this study, we will systematically vary key parameters or assumptions within our analytical framework to assess their impact on the study outcomes. This may involve testing different statistical models, criteria for participant inclusion/exclusion, handling of missing data, or adjustments for potential confounding variables. By exploring a range of scenarios, we aim to evaluate the robustness of our findings and assess the degree to which they are influenced by specific methodological choices or assumptions. Sensitivity analysis allows us to identify the potential sources of uncertainty and to provide a more comprehensive understanding of the reliability and generalizability of our study results.

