## Objectives

The **main objective** of this research is to quantify and characterize the PV found in MGPT of GC patients in Alto Alentejo (Portugal).

The **specific objectives** are:

- Determine the global rate of PVs in GC patients of Alto Alentejo;
- Determine which PVs are most common in our GC population;
- Correlate the PVs found with clinical factors: Age at diagnosis; Sex; Weight; Height; Presence of other diseases (Diabetes; Arterial Hypertension; Dyslipidaemia; Stroke; Heart attack); Date of diagnosis; Stage at diagnosis; Histologic subtype; Surgery for GC; Personal history of other cancers; Familial history of GC and other cancers;
- Correlate the PVs found with prognostic factors: 12-month survival rate; mortality.

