#### **Study size**

The sample calculation takes into account the number of annual cases of GC recorded in Alto Alentejo (65 cases in 2020, data from National Oncologic Registry). Therefore, the sample calculation suggests that it should include 56 patients with GC, with a confidence level of 95% and a margin of error of 5%.

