**Table 2 - Variables / Measurements**

Type of Variable	Name of Variable	Measurements
MGPT Outcomes variables	MGPT	positive (1) or negative (0)
	PV	integer number
	Likely pathogenic variables (LP)	integer number
	Name of genes with PV	descriptive
	PV in each gene	integer number
	VUS	integer number
Potential confounders variables	Age at diagnosis	Years
	Sex	Female(1)/Male(0)
	Weight	Kg
	Height	cm
	Body mass index	Kg/m 

	Presence of other diseases: Diabetes; Arterial Hypertension; Dyslipidaemia; Stroke; Heart attack);	Yes(1)/No(0) for each disease
	Stage at diagnosis (AJCC staging system);	0, I, IIa, IIb, III, IVa, IVb
	Histologic subtype;	Intestinal (1); Diffuse (2); Mixed (3)
"Exposures" variables	Personal history of other cancers	Yes (1)/No (0)
	Types of other cancer in GC patient	descriptive
	Familial history of GC	Yes (1)/No (0)
	Age of onset of each familial case of GC	integer number
	Familial history of other cancers (specifying)	descriptive
	Age of onset of each familial case of other cancers	Years
Prognostic related variables	12-months survival	Yes (1)/No(0)
	Death due to GC	Yes (1)/No(0)
	Date of death	mm/yyyy
Other variables:	Date of diagnosis	mm/yyyy
	Localization of tumor	Cardia / Fundos / Body / Antrum/pyloro
	Time since diagnosis until the current moment	months
	Surgery for GC	Yes (1)/No (0);
	Type of surgery	Total gastrectomy (1); Subtotal gastrectomy (0)
	Date of Surgery	mm/yyyy
	Histologic staging after surgery	0, I, IIa, IIb, III, IVa, IVb
	Underwent chemotherapy	Yes (1) / No (0)
	Type of chemotherapy	descriptive

	Cycles of chemotherapy	integer number
	Positive MGPT is considered when it is found at least one PV in one gene of teste	A comparative analysis will be made between the individual characteristics and tumor characteristics of positive MGPT cases with those with negative MGPT.

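### Stage is recorded on an ordered scale, but by default it falls under tests that ignore the order; an ordinal method with an effect measure should be named, although power stays low with few carriers

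*Combined protocol and SAP*

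**What the plan says.** The Objectives list the clinical factors to be related to pathogenic variants (PVs), among them "Date of diagnosis; Stage at diagnosis; Histologic subtype; Surgery for GC". Table 2 has two stage variables, "Stage at diagnosis (AJCC staging system" and "Histologic staging after surgery", both coded "0, I, IIa, IIb, III, IVa, IVb".

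Statistical methods, item b, offers two routes. Quantitative variables go to the t-test or, if not normal, the Mann-Whitney test. For the rest: "For qualitative variables, the statistical significance of the difference between groups, with 95% CI, will be calculated using the Chi-square test" or Fisher's exact test. The condition for choosing between these two is "if more than 10% of the cells in the 2x2 tables have frequencies" of 5 or less. No ordinal or trend test is named, and no grouping of stages is set.

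The section on quantitative variables says that every quantitative and qualitative variable will be compared between MGPT-positive and MGPT-negative patients. It plans effect measures with 95% CIs, and inferential tests only where possible.

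**The concern.** Whether carriers present earlier or later than non-carriers is a question about order. Chi-square and the exact unordered test treat the seven stages as interchangeable labels. They spread a handful of carriers over seven cells and spend 6 degrees of freedom on differences of any shape, so a consistent shift in one direction is diluted. An unordered 2x7 comparison also gives a p-value but no single measure of how far the groups differ, so it does not deliver the effect measure with CI that the plan promises. The condition on 2x2 tables does not fit a 2x7 table either. Whichever of the two tests it selects, the order is lost.

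**Working it through.** **1. The plan's own figure.** Study size says that "it should include 56 patients with GC, with a confidence level of 95% and a margin of error of 5" per cent, based on "65 cases in 2020, data from National Oncologic Registry". With p = 0.5 (assumed, not stated) and a finite population correction:

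n0 = 1.96² × 0.25 / 0.05² = 384.1

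n = 384.1 / (1 + 383.1/65) = 55.7, rounded up to 56.

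The figure reproduces. It is a precision calculation for one proportion and contains no power for any comparison between groups.

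**2. Number of carriers.** Risks and Benefits cites 3-5% hereditary cases: 0.03 × 56 = 1.7 and 0.05 × 56 = 2.8, so 2 or 3 carriers. The Introduction can be read as 3-5% of the familial 20%, which gives at most 0.05 × 0.20 × 56 = 0.6. The study also allows that prevalence may be higher, so up to 11 carriers (20%) are considered below as an assumption.

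**3. Sparseness.** Take an assumed stage mix of 3/22/12/13/22/8/20% and 5 carriers. The expected carrier counts are 5 × mix = 0.15, 1.10, 0.60, 0.65, 1.10, 0.40, 1.00. No cell exceeds 1.1.

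**4. Power under that mix.** Simulation with n = 56, two-sided 0.05 (assumed from the 95% CIs) and a proportional-odds shift. The unordered test is the permutation chi-square and the ordinal test is the permutation rank test.

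| Shift | Carriers | Odds ratio | Unordered | Ordinal | Ratio |
|---|---|---|---|---|---|
| Later | 3 | 4 | 6% | 21% | 3.5 |
| Later | 3 | 8 | 7% | 41% | 5.9 |
| Later | 5 | 4 | 7% | 32% | 4.6 |
| Later | 5 | 8 | 19% | 58% | 3.1 |
| Later | 8 | 4 | 18% | 49% | 2.7 |
| Later | 8 | 8 | 41% | 82% | 2.0 |
| Earlier | 3 | 4 | 15% | 23% | 1.5 |
| Earlier | 5 | 4 | 17% | 35% | 2.1 |
| Earlier | 5 | 8 | 35% | 64% | 1.8 |
| Earlier | 8 | 4 | 21% | 50% | 2.4 |
| Earlier | 8 | 8 | 52% | 83% | 1.6 |

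Type I error was about 4-6% for both tests. Repeat runs differed by a few percentage points. With 800 runs, the standard error at 30% power is √(0.3 × 0.7/800) = 1.6 points.

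**5. Other stage mixes.** Odds ratio 5, shift to later stage, exact unordered (Fisher-Freeman-Halton) against exact Mann-Whitney:

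- Even mix: 9.4% vs 26.7% (3 carriers), 20.8% vs 53.5% (6), 34.7% vs 73.9% (11). Ratios 2.8, 2.6, 2.1.
- Mix weighted to late stage (2/15/12/13/25/13/20%): 4.0% vs 25.5%, 14.2% vs 48.8%, 31.8% vs 73.7%. Ratios 6.4, 3.4, 2.3.

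With 3 carriers and the late-weighted mix, the ratio at odds ratio 10 is 46.6/6.2 = 7.5, so about 7-fold is the upper end for odds ratios up to 8.

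**6. Why direction matters.** In step 3, one carrier in stage 0 adds (1 − 0.15)²/0.15 = 4.8 to chi-square, while one carrier in stage IVb (expected 1.0) adds nothing. Under that mix the unordered test therefore reacts more to an earlier shift, and the ordinal test gains less. Under an even mix the two directions are equivalent by symmetry, so the difference between directions comes from the uneven mix.

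**7. Limit of the gain.** With 3 carriers the ordinal test still misses 100 − 21 = 79% of shifts at odds ratio 4 and 59% at odds ratio 8. With 2 carriers its power is 8% and 15%. At odds ratio 2, unordered against ordinal power is 4% vs 7% (3 carriers) and 6% vs 13% (5 carriers). At odds ratio 3 the ordinal test reaches only 40-43% even with 11 carriers.

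**The case against.** Four fair points can be made in favour of the plan.

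**Few carriers are the main limit.** A reader might infer that a real stage shift would be missed because of the choice of test. The documents' own 3-5% does not support that: with 2 or 3 carriers the ordinal test also usually misses the shifts considered. This stands. The choice of test makes a practical difference mainly if prevalence proves higher than cited and the shift is large.

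**Nothing says that a non-significant test will be read as no association.** A reader might infer it, but the plan puts effect measures with 95% CIs first and tests only where possible. This stands as a limit on the harm. It does not remove the point, because an unordered 2x7 test supplies no single effect measure.

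**The plan never states that stage will be tested as an unordered 2x7 table.** Its wording on 2x2 tables could mean that stages will be grouped, and its sensitivity analyses foresee other statistical models. This stands in part. No grouping and no ordinal model is named, so the unordered test is the default route. A grouping left open could also be chosen after the data are seen.

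**The assumed shifts are large.** Nothing in the documents supports odds ratios of 4 to 8 or any particular stage mix. This stands. The ratios show the direction and rough size of the gain; they are not predictions.

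**Conclusion.** The point holds as a cheap improvement of minor weight. By default, stage falls under tests that ignore its order and do not yield the planned effect measure with CI. An ordinal method uses the same data better, in both directions of shift, under every stage mix tried and at a similar type I error. For odds ratios of 4 to 8 with 3 to 8 carriers the gain in power is about 2- to 7-fold for a later-stage shift. For an earlier-stage shift it is about 1.5- to 2.5-fold under the uneven mix, and a little more (up to 2.8-fold at odds ratio 5) if the mix is even.

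These figures rest on assumptions absent from the documents: the stage mix, proportional odds, the size of the shift, the carrier counts above 3 and two-sided 0.05. The documents do not support a stronger claim that the choice of test would decide the finding on stage, or that the investigators would report no association. The weight is minor because the main objective is to quantify and characterise PVs, which this does not affect, and stage is one of many factors under an exploratory specific objective.

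**What to change.** Add to Statistical methods, item b:

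> Stage at diagnosis and histologic stage after surgery are ordinal. They are compared between MGPT-positive and MGPT-negative patients by the exact Mann-Whitney test (or exact linear-by-linear association test), reported with a common odds ratio or probability of superiority and its 95% CI. With few carriers, a non-significant result is not evidence of no association.

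The plan should fix one of the two tests and one of the two measures before the data are analysed, which also closes off a choice of stage grouping after the fact. The cost is one short addition and no new data, and Mann-Whitney is already in the plan for quantitative variables. The downside is less sensitivity to a non-monotone pattern, such as carriers concentrated in the middle stages. A table of stage counts by MGPT result, shown beside the test, would let a reader see such a pattern.

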#### **Quantitative variables**

For quantitative variables we will do the descriptive statistics analyses with mean, mode, median, standard deviation, interquartile variation, maximum and minimum.

Subgroup analysis will be carried out, for each quantitative and qualitative variable, dividing patients who have positive or negative MGPT. We will analyse the effect measures of the difference between the two groups, with confidence interval (IC) 95%, and if possible, inferential statistical analysis will be conducted.

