### **Risks and Benefits**

The main benefits and expected outcomes of the study are the contribution to a better understanding of GC carcinogenesis, which could improve the diagnostic and therapeutic approach of GC patients and their relatives. In addition, this research may help to clarify whether the prevalence of hereditary GC is higher than that described in the literature (3-5%) (4,5), and may justify screening the population for this disease.

However, the use of MGPT is not without important risks, namely the identification of variants of undetermined significance (VUS), which requires careful integration of all clinical and genetic information for correct personal and family counselling. Whenever necessary, VUS carriers (as well as patients with identified PVs) will be referred to the Portuguese Institute of Oncology in Lisbon (IPOLFG) for family risk and genetic counselling. Other potential risks of this study include the psychological stress and anxiety caused by the survey and MGPT results, the need to travel to participate in the study, and the fact that the study is being conducted by non-geneticist researchers, which limits the immediate counselling that can be provided. In this way, we will have the collaboration of the psychologists of the Day Hospital, and our close collaboration with the Germano de Sousa Genetics Laboratory and the IPOLFG teams will allow an adequate response to technical questions about the MGPT. Finally, it should be noted that this observational study will only analyse the MGPT results of CG patients and will not propose any additional intervention for patients or their families.

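### The chi-square/Fisher rule is reversed as written: 2x2 tables with small cells go to chi-square and the others to Fisher's exact test

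*Combined protocol and SAP*

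**What the plan says.** Statistical methods (b) sets the test for qualitative variables when MGPT-positive and MGPT-negative patients are compared. It names the "Chi-square test (if more than 10% of the cells in the 2x2 tables have frequencies" of 5 or less, "or the Exact Fisher Test". The small-cell condition is attached to chi-square, and Fisher's test is left for the remaining tables.

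The rule has wide reach. Under Quantitative variables, the subgroup analysis is to be done "for each quantitative and qualitative variable, dividing patients who have positive or negative MGPT", although "if possible, inferential statistical analysis will be conducted". Table 2 defines the grouping: "Positive MGPT is considered when it is found at least one PV in one gene of teste". Study size says that "it should include 56 patients with GC". Risks and Benefits cites 3-5% as the literature prevalence of hereditary gastric cancer.

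**The concern.** The chi-square test relies on a large-sample approximation that needs adequate expected counts. When counts are small, the exact test is the remedy. The written rule does the opposite, and no other section of the protocol states or corrects it.

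The rule decides the tests for two of the four specific objectives: the correlations of pathogenic variants with clinical factors and with prognosis. Table 2 has 13 two-level variables that would be compared by MGPT result: sex, five comorbidities, personal history of other cancers, familial history of gastric cancer, surgery, type of surgery, chemotherapy, 12-month survival and death due to gastric cancer. With few positives, nearly all of these tables are sparse. Some associations could then be declared significant only because the wrong test was prescribed. The other two objectives, the overall variant rate and the most common variants, are not affected.

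Two details of the same sentence are also open. It does not say whether *frequencies* means observed or expected counts. It also covers only 2x2 tables, whereas stage at diagnosis (7 levels), staging after surgery (7), tumour location (4) and histologic subtype (3) are larger and have no test rule.

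**Working it through.** **Inputs.** N = 56 (Study size); 3-5% (Risks and Benefits); the trigger of more than 10% of cells at 5 or less (Statistical methods (b)). Yields of 10%, 15% and 20% are my assumptions, added to show a range. The significance level is taken as two-sided 5%, matching the 95% confidence level.

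**1. The planned sample size reproduces.** With p = 0.5 (assumed, not stated), a 5% margin and a population of 65:

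- n0 = 1.96² × 0.25 / 0.05² = 384.15
- n = 384.15 / (1 + 383.15/65) = 55.7, rounded up to 56

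**2. What triggers chi-square.** A 2x2 table has four cells. One small cell is 1/4 = 25%, above 10%, so a single small cell is enough.

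**3. When a small cell is unavoidable.** Let m be the number of positives and s the number of patients with the factor.

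- Observed counts: the two cells of the positive row add to m. If m ≤ 11, one of them must be 5 or less. At m = 12 a 6/6 split avoids it.
- Expected counts: the smaller expected count in the positive row is m × min(s, 56−s)/56, at most m/2. It is always 5 or less if m ≤ 10. At m = 11 and s = 28 it is 5.5.

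So Fisher's test can be reached only with at least 12 positives (observed reading) or 11 (expected reading).

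**4. How likely that is.** With X ~ Binomial(56, yield):

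| Yield | Expected positives | P(X ≥ 12) | P(X ≥ 11) |
|---|---|---|---|
| 3% | 1.7 | 9 × 10⁻⁸ | 8 × 10⁻⁷ |
| 5% | 2.8 | 1.7 × 10⁻⁵ | 9 × 10⁻⁵ |
| 10% | 5.6 | 0.8% | 2.1% |
| 15% | 8.4 | 12.5% | 21% |
| 20% | 11.2 | 45% | 58% |

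**5. A hypothetical table.** Three positives, factor present in 2/3 versus 8/53:

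- Uncorrected Pearson: 56 × (2×45 − 1×8)² / (3×53×10×46) = 56 × 82² / 73,140 = 5.15, p = 0.023
- Continuity-corrected: 56 × (82 − 28)² / 73,140 = 2.23, p = 0.135
- Fisher, two-sided: [C(10,2)×46 + C(10,3)] / C(56,3) = (2,070 + 120)/27,720 = 0.079

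Only the uncorrected chi-square is significant at 5%.

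**6. True size of each test.** For fixed m and s the positive-row cell is hypergeometric under no association. I summed the probabilities of all tables with p ≤ 0.05, for s = 3 to 53 (51 values).

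- Uncorrected Pearson, m = 3: average size 4.6%. It exceeds 5% for 20 of the 51 counts (39%) and is zero for s = 26 to 30. The peak is 15.5%, at s = 3 and s = 53. For s = 3 this is 1 − C(53,3)/C(56,3) = 1 − 23,426/27,720. Elsewhere the maximum is 11.3%.
- Uncorrected Pearson, m = 2 to 11: between 15 and 25 of the 51 counts exceed 5%, with peaks of 8% to 17%.
- Continuity-corrected, m = 2 to 11: never above 4.2%.
- Fisher, m = 2 to 11: never above 5%. The average is 1.4% with 3 positives and 2.3% with 6.

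**The case against.** The strongest reply is that this is a drafting slip. The sentence names both tests and a small-cell threshold, and the parenthesis probably sits after the wrong test. That is plausible, but the text is the prespecified rule. If the analyst follows it, sparse tables get the wrong test. If the analyst departs from it, the choice of test is undocumented.

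Second, the harm is modest and conditional. Uncorrected Pearson averages below 5%, most factor counts show no excess, and continuity correction removes the excess for 2 to 11 positives. This stands, and it limits the severity. It does not justify the rule, because the plan does not say which version is meant.

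Third, 3-5% is a literature prevalence of hereditary disease, not the yield of these 15- and 30-gene panels in patients chosen by multidisciplinary consultation. This also stands. At 20% the exact test could be reached in up to 45% or 58% of studies, so the claim that Fisher would practically never be used holds only near the cited rate. Conversely, Background can be read as applying 3-5% only to the up to 20% of patients with familial aggregation. That would be 0.6% to 1% of all patients (0.2 × 3% to 0.2 × 5%), with still fewer positives.

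Fourth, with no positives or only one, the choice of test is not the main obstacle. The chance of this is 50% at a 3% yield and 22% at 5%. With a single positive, Fisher cannot reach 5% for any of the counts examined, while even the corrected chi-square reaches a size of 5.4% at its maximum. The plan already makes inference conditional on feasibility.

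Fifth, chemotherapy and type of surgery are not listed under Objectives and enter only through the instruction to compare every variable. Type of surgery also applies only to operated patients, so the N = 56 figures do not describe that table.

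None of these points touches the reversal itself.

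**Conclusion.** The concern holds. The condition in Statistical methods (b) is the reverse of what the chi-square approximation requires, whatever the origin of the wording. This conclusion rests on the text alone and needs no assumption about yield.

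Its practical size depends on two things. The first is the number of positives: near the cited 3-5%, the written rule sends essentially every 2x2 comparison to chi-square, and at an assumed 20% it sends roughly half or more. The second is the version of chi-square: uncorrected, the size can reach about three times nominal (15.5% with 3 positives) for some factor counts, while on average it stays just under 5%. The point should be fixed before analysis. It does not threaten the estimate of the variant rate.

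**What to change.** Replace the rule with a sentence such as: *Chi-square will be used only if all expected counts are at least 5; otherwise Fisher's exact test will be used (Fisher-Freeman-Halton for tables larger than 2x2, such as stage, histologic subtype and tumour location).* State also whether chi-square is continuity-corrected.

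Simply moving the existing condition to Fisher's test would cure the reversal. It would leave open whether counts are observed or expected, and what is done with the larger tables. The threshold of 5 for all expected counts is a common convention and not the only defensible one.

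At N = 56 the proposed wording sends every 2x2 table to Fisher when 9 or fewer patients are positive, since the smaller expected count is then at most 9/2 = 4.5. Sample size and data collection do not change. The cost is power: Fisher is conservative here (average size about 1.4% with 3 positives and 2.3% with 6), so some p-values will be less favourable.

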## Introduction

**Background/ Rationale** According to data from the Global Cancer Observatory, gastric cancer (GC) ranks fifth in terms of incidence and mortality worldwide (1).

It is a multifactorial and heterogeneous disease involving both environmental and genetic factors. Although the majority of cases are sporadic, caused by environmental exposures, up to 20% of patients have a familial aggregation and of these, 3 to 5% are classified as hereditary with an identified mutation (8,9).

Three hereditary syndromes primarily affect the stomach: Hereditary Diffuse Gastric Cancer (HDGC); Gastric Adenocarcinoma and Stomach Proximal Polyposis (GAPPS); and Familial Intestinal Gastric Cancer (FIGC) (2). HDGC is an autosomal dominant syndrome, predominantly caused by germline mutations in the *CDH1* gene, which encodes the e-cadherin protein with important functions in cell aggregation, and is characterised by a high risk of early-onset diffuse GC and invasive lobular breast cancer (10). GAPPS is caused by germline mutations in *APC* promoter 1B and is characterised by the presence of fundic gland polyposis with focal dysplasia and intestinal or mixed adenocarcinoma at the level of the gastric fundus and sparing the antrum (4,11). Finally, FIGC is an autosomal dominant syndrome, still poorly characterized genetically, which is associated with an increased risk of intestinal GC (10).

Other genetic syndromes are also associated with an increased risk of GC. Some of the genes involved include *MLH1*, *MSH2*, *MSH6*, and *PMS2* (Lynch Syndrome - LS), *TP53* (Li-Fraumeni Syndrome), *APC* (PAF and ADC / proximal polyposis of the stomach) and *MUTYH* (Polyposis Associated MUTYH), *BMPR1A* and *SMAD4* (Juvenile Polyposis Syndrome), *STK11* (Peutz-Jegher Syndrome) and *PTEN* (Cowden Syndrome) (3–5).

As GC is a neoplasm with numerous somatic and hereditary mutations involved in its carcinogenesis, the use of MGPT can be crucial, as it performs the analysis of hereditary mutations in a significant number of genes simultaneously (depending on the genes included in the panel) (6,7). In addition to the described mutations, MGPT has allowed the identification of new genetic mutations associated with GC risk, including in the *BRCA 1/2*, *PALB2*, *ATM* and *RAD51C* genes (typically associated with hereditary breast and ovarian cancer), *MAP3K6*,

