### Setting

This study takes place at the Unidade Local de Saúde do Alto Alentejo (ULSAALE). The MGPT was always performed in the same laboratory (Germano de Sousa – Centro de Genética Laboratorial) using peripheral blood samples from patients with GC.

Two types of MGPT were used:

- MGPT 4005 (15 genes): APC, ATM, BLM, BMPR1A, CDH1, CTNNA1, EPCAM, MLH1, MSH2, MSH6, PMS2, PTEN, SMAD4, STK11/TP53.
- MGPT 4013 (30 genes): ATM, BARD1, BLM, BRCA1, BRCA2, BRIP1, CDH1, CHEK2, EPCAM, FANCC, MLH1, MRE11A, MSH2, MSH6, MUTYH,

NBN, NF1, PALB2, PMS2, PTEN, RAD50, RAD51C, RAD51D, RECQL4, RINT1, SLX4, SMARCA4, STK11, TP53, XRCC2.

The majority of patients with GC were tested with MGPT 4005. Patients with neoplasms other than GC or with a family history of other neoplasms were tested with MGPT 4013. The decision to perform MGPT and the choice of panel type were made in multidisciplinary consultation.

The recruitment process takes place between January 2023 and December 2024. All data will be collected and entered in a database until September 2025

The manuscript for publication will be written between October and November 2025.

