#### **Bias**

Efforts to address potential sources of bias:

**Clear Inclusion and Exclusion Criteria:** The inclusion criteria are clear to select patients that are representative of the target population (patients with gastric adenocarcinoma) and that there is no bias in participant selection.

**Control of Confounding Factors:** There are some confounding factors that may influence the study results, such as age, sex, Weight; Height; Body mass index; **Presence of other diseases:** Diabetes; Arterial Hypertension; Dyslipidaemia; Stroke; Heart attack). This will be achieved through appropriate statistical techniques or data stratification during analysis.

**Uniformity in data records:** There was uniformity in the data recorded for each participant who agreed to be submitted to MGPT, minimizing the variability between records or the missing clinical data.

**Consistent and Accurate Data Collection:** This will be achieved through adequate training of interviewers or data collection personnel and the use of standardized data collection protocols.

**Blind Data Assessment:** After collection, the data will be pseudo-anonymized so that the researcher who analyses the data will not have access to the patient's identifying data.

**Time-Sensitive Analysis:** Data analysis takes into account the timing of data collection relative to relevant clinical events.

**Sensitivity Analysis:** It will be performed a sensitivity analyses to assess the robustness of the results across different results of MGPT and clinical factors.

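### The adjusted logistic regression has no final covariate set, sparse-data method or model for the prognostic objective, so adjusted odds ratios may not exist if few panel tests are positive

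*Combined protocol and SAP*

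**What the plan says.** The adjusted analysis is one sentence in Statistical methods (b): "We will later perform a multivariate analysis with logistic regression to control confounding variables". It follows directly on the unadjusted comparisons of positive with negative MGPT.

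The Bias section introduces the adjustment variables by example: "There are some confounding factors that may influence the study results, such as age, sex, Weight; Height; Body mass index", followed by five diseases, which makes ten. It then says "This will be achieved through appropriate statistical techniques or data stratification during analysis". Table 2 heads a longer list as potential confounders, adding seven-level stage and three-level histologic subtype. It places MGPT result under outcomes, and personal and family cancer history under exposures.

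One specific objective points the other way, with PV status as the explanatory variable: "Correlate the PVs found with prognostic factors: 12-month survival rate; mortality".

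The target is that "it should include 56 patients with GC". The only small-sample provision is Fisher's exact test, for unadjusted tables. Quantitative variables makes inference conditional on its being possible, and Statistical methods (d) mentions trying other models. Neither gives a threshold or a named alternative.

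**The concern.** When PV carriers are few, they may all fall on one side of a factor or of a combination of covariates. The maximum likelihood odds ratio for at least one term is then infinite (separation). Software may still print a very large coefficient and standard error, and the analyst must choose, with the data in view, what to drop or merge.

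The specific objectives at stake are those that relate PVs to clinical factors and to prognosis. Their adjusted results could be unusable or depend on choices made afterwards, while the Bias section promises that confounding will be controlled. The PV rate and the description of which variants occur do not depend on the regression.

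**Working it through.** **Study size.** The 56 reproduces. With a proportion of 0.5 (assumed, not stated), n0 = 1.96² × 0.25 / 0.05² = 384.1. Corrected for 65 annual cases, 384.1 / (1 + 383.1/65) = 55.7, rounded up to 56. This sizes the precision of a proportion and says nothing about a regression.

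**Expected positives, 56 × rate.** The 3-5% is the literature rate for hereditary gastric cancer in Risks and Benefits; 10% and 20% are assumptions.
- 3%: 1.7
- 5%: 2.8
- 10%: 5.6
- 20%: 11.2

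**A check by hand.** Take k positives and a binary factor present in a share q of patients. The unadjusted odds ratio is infinite or zero when all positives fall on one side, with probability about q^k + (1−q)^k. With q = 0.30 (assumed):
- k = 2: 0.09 + 0.49 = 0.58
- k = 3: 0.027 + 0.343 = 0.37
- k = 6: 0.001 + 0.118 = 0.12
- k = 11: 0.02

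Rarer factors do worse. At 6 and 11 positives, q = 0.20 gives 0.26 and 0.09; q = 0.07 (assumed for stroke or heart attack) gives 0.65 and 0.45.

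**Simulation, positive MGPT as outcome.** n = 56, no true effects, 1,000 datasets per setting, separation tested by linear programming, Monte Carlo error up to 3 points. Assumed covariates: age mean 70 (SD 11), 40% female, height 165 cm (SD 9), BMI 26 (SD 4), weight derived from these, diabetes 25%, hypertension 55%, dyslipidaemia 40%, stroke 7%, heart attack 7%; binary factor 30%. Percentage of datasets with separation:

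| Terms in model | 2 positives | 3 | 6 | 11 |
|---|---|---|---|---|
| One binary factor + age | 58 | 36 | 13 | 2 |
| Age, sex, BMI | 52 | 28 | 5 | 0.2 |
| Age, sex, BMI, diabetes, hypertension | 91 | 74 | 25 | 4 |
| All ten named in Bias | 100 | 99 | 91 | 73 |

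A repeat gave 60/34/13/4 for the first row, 56/28/4/0.3 for the second and 100/99/94/77 for the last. Leaving out weight and height barely changes the last row (99.9/99.4/90.7/72.9).

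**A larger sample.** The Setting section says "The recruitment process takes place between January 2023 and December 2024". If every case in two years were tested, 2 × 65 = 130 patients would give about 4/6/13/26 positives at the same rates. The ten-term model then separates in 97/91/65/25%.

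**Prognostic models.** With 12-month survival as outcome, 40% deaths assumed and PV status as the factor, separation at 2/3/6/11 carriers is 52/26/6/1% for PV plus age and 72/61/48/49% for PV plus ten terms. The hand formula agrees for PV alone: 0.6² + 0.4² = 0.52 at 2 carriers and 0.6³ + 0.4³ = 0.28 at 3.

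**What Firth regression would give.** For one factor plus age, profile-likelihood intervals were finite in every simulated dataset, with null coverage of 93-100%. They are wide. Median ratio of upper to lower limit at 2/3/6/11 positives:
- binary factor: 1783/108/34/18
- weight per SD: 16/10/5/4
- stage in two groups (0-II v III-IV): 1775/97/31/15
- seven-level stage (IVb v I): 4456/3483/2070/113

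**The case against.** The strongest reply is that the plan is less silent, and the counts less certain, than they look.

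- **Outcome.** A reader might infer that no model outcome is indicated at all. That goes too far. Table 2 and the comparisons just before the regression sentence suggest positive MGPT as outcome, with cancer history among the factors. What is missing is the final covariate set, a rule for sparse data and a model for prognosis.
- **Rate.** A reader might take 3-5% as the expected yield. It refers to hereditary gastric cancer, whereas a positive MGPT is any PV on a 15- or 30-gene panel, so the yield may be higher. The Introduction's wording, "up to 20% of patients have a familial aggregation and of these, 3 to 5% are classified as hereditary with an identified mutation", read literally gives 56 × 0.20 × 0.03 to 0.05 = 0.3 to 0.6 positives. That too is not a planning rate for panel results, and the point should not rest on it.
- **Model size.** A reader might infer that a ten-term model is planned and must fail. The list is given as examples, and nothing says that all ten enter one model.
- **Flexibility.** Making inference conditional and mentioning other models does allow for trouble. It does not say when to change course, or to what.

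The first three narrow the point. They do not remove it: the plan does not commit to a small model, and at 2-3 positives even a very small one often fails.

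**Conclusion.** The point holds in this limited form, as a cheap improvement to the secondary analyses. The plan relies on ordinary logistic regression with 56 patients and has no provision for few positives. At 2-3 positives, one binary factor plus age has no finite maximum likelihood solution in roughly 35-60% of datasets. At 6-11 positives the simulated small models fail in about 0-13%, more for rare factors, while a ten-term model would fail in about 70-90%.

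These figures rest on assumed covariate frequencies, no true effects and a positive rate that the documents do not state. It would be wrong to conclude that the main objective is threatened: the PV rate is unaffected.

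**What to change.** Replace the regression sentence in Statistical methods (b) with:

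> Adjusted analyses use Firth penalised logistic regression with profile-likelihood 95% CIs: (1) positive MGPT as outcome, one clinical factor at a time; (2) 12-month survival and, separately, death due to GC as outcome, with positive MGPT as the factor. Each model has at most one further prespecified covariate, and the unadjusted estimate is reported beside the adjusted one. Weight, height and BMI are never entered together, and stage is collapsed to prespecified broad groups. With fewer than 2 positive MGPTs no model is fitted and carriers are described. Adjusted results are exploratory and confounding is not claimed to be controlled.

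Amend the Bias section to match.

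**Choice of covariate.** If it is age at diagnosis, note that the Introduction describes the *CDH1* syndrome as "characterised by a high risk of early-onset diffuse GC and invasive lobular breast cancer". Age may therefore itself reflect PV status, which is one reason to show the unadjusted estimate.

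**Panel type.** Setting says that the 30-gene panel went to patients with other neoplasms or a family history of them, so the chance of finding a PV depends on those factors by design. When personal or family cancer history is the factor, restrict the MGPT outcome to the genes on both panels (11 by the lists in Setting), or report by panel.

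**Minimum count.** A higher minimum such as 6 may appeal, because that is where Fisher's test on a 28/28 factor can first reach p < 0.05 (0.052 at 5, 0.023 at 6). For less even splits this happens sooner: at 2 positives for 4/52, 3 for 14/42, and 4 for 22/34 or 25/31. A minimum of 6 would also stop modelling in 99% and 94% of samples of 56 at rates of 3% and 5%. A minimum of 2 does so in 50% and 22%, and in 2% at a rate of 10%.

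**Cost.** Wording, plus one procedure. Confirm that the SPSS installation supports Firth regression or name a second program, and state how profile-likelihood intervals are pooled after multiple imputation. Intervals will be wide, there will be fewer adjusted estimates, and restricting to shared genes may lower the count of positives further.
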